1. INTRODUCTION AND RATIONALE

Wheat has been used for millennia as a raw material for basic foods and is generally known as a health promoting cereal grain, providing an important contribution to daily energy intake and nutrients worldwide. This is partly due to its favourable nutritional composition which provides a good source of dietary fibres as well as vitamins and minerals (1). The evidence about the health benefits of consuming whole grain foods made from wheat, oat, barley and rye is rather consistent. It is associated with reduced risk of type 2 diabetes, cardiovascular disease, obesity as well as cancer (2-7). However, gluten-containing cereals may also elicit adverse physical reactions (e.g. coeliac disease, wheat allergy) in susceptible individuals. Coeliac disease is a chronic, small-intestinal immune-mediated enteropathy initiated by exposure to dietary gluten in genetically predisposed individuals, with a prevalence of 0.5-1% in the general population (8). Wheat allergy is a distinct entity, characterized by an IgEmediated allergic response to wheat with a prevalence of 0.2% (9). In addition, there is a large proportion of the general population (0.5-30%) that avoid or reduce gluten-containing products, despite the fact that e.g. coeliac disease and/or allergy have been ruled out (10-14). This phenomenon is referred to as non-coeliac gluten sensitivity (NCGS) or non-coeliac wheat sensitivity (NCWS) and manifests as gastrointestinal (GI) (e.g. abdominal discomfort, bloating, diarrhoea, rumbling, pain) and/or extra-intestinal complaints (e.g. headache, lethargy, depression, anxiety) soon after consuming wheat or gluten, which improve after gluten/wheat withdrawal (14). The biological rationale leading to symptoms in NCGS or NCWS is limited. Increasing evidence indicates that NCGS may also be affected by psychosocial factors, in part fuelled by articles in the lay press and social media. Information is emerging that glutencontaining products can cause medical and psychological symptoms, with a link to the belief that our body has not sufficiently evolved to adapt to grains in our diet. As a consequence, more and more people embrace a gluten-free diet, especially with regard to the consumption of (wheat/gluten-containing) bread. Although some replace wheat-based food products with oat products that do not contain gluten but are rich in fibers and micronutrients, others adjust their diet without adequate replacement, which may lead to unbalanced dietary intake and nutrient deficiency (15).

So far, studies on eliminating wheat or gluten-containing products from the diet showed some beneficial effects, but are mostly based on uncontrolled designs. The review of Catassi *et al.* (16) indicates that the absence of a clear biological mechanism of action in which psychological factors may also play a role, have immersed NCGS into even deeper controversy. A double-blind placebo-controlled crossover study by Biesiekierski *et al.* (17) showed a significant worsening of overall symptoms and pain irrespective of the diet (*i.e.* placebo, low-gluten or high-gluten diet) and markedly, the symptom scores were highest with the first treatment they

received. It is also remarkable that all the participants resumed to a gluten-free diet (GFD) at the end of the trial as they "report feeling better". These findings indicate that psychological factors and expectation mediate placebo and nocebo effects by influencing GI sensory and motor functions along the bidirectional brain-gut axis (18). However, studies examining the contribution of a negative expectation leading to symptoms when consuming gluten has never been investigated. Therefore, we aim to examine, in a randomized, double-blind, controlled study, whether expectancy of consuming gluten will impact on overall intestinal and extraintestinal symptoms in individuals with NCGS. With this study we will gain important insights in the effects of different types of bread on GI health, which may highlight the importance of considering the nocebo effect and eventually will help to make dietary recommendations in NCGS.

2. OBJECTIVES

Primary Objective:

In this randomized, double-blind, controlled study, we aim to investigate the effects of consumer expectancy, related to either gluten-containing or gluten-free oat bread on short-term (within 8 hours) overall GI symptoms in individuals with NCGS.

Hypothesis:

We hypothesize that expected gluten intake via bread consumption (as influenced by verbal information), but not the actual gluten intake increases subjective overall GI symptom score in individuals with NCGS. (see Figure 1, comparison E+G- vs. E-G-).

Expectation Intervention

[figure not shown]

Figure 1. Overview of group comparison related to the primary objective (*i.e.* comparing E-G- vs. E+G- groups). (E- = Expectancy of getting gluten-free bread, E+ = Expectancy of getting gluten-containing bread, G + = actual gluten-containing bread, G- = actual gluten-free bread).

Secondary Objective(s):

 To investigate the effects of the actual intake of gluten on overall symptoms in individuals with NCGS.

Hypothesis:

We hypothesize that expected bread consumption (E+ or E-) (as influenced by verbal information), but not the actual bread composition (G+ or G-) affects subjective GI and extra-intestinal symptoms in individuals with NCGS.

- To investigate the effects of expected gluten intake and actual gluten intake on individual GI and extra-intestinal symptoms in individuals with NCGS.

Hypothesis:

We hypothesise that in participants who expect to receive gluten-containing bread, there will be an increase in GI and extra-intestinal symptoms regardless of the actual bread composition (G+ or G-) in individuals with NCGS.

- To study the impact of emotional well-being on overall, intestinal and extra-intestinal symptoms after expected or actual gluten intake in individuals with NCGS.

Hypothesis:

We hypothesize that individuals with decreased emotional well-being (as measured by PHQ-9, PHQ-15 and GAD-7) are more vulnerable to expectation in relation to gluten intake (as influenced by verbal information) leading to more symptoms.

- To investigate the effects of expectation and/or actual intervention on mood (affective) changes in individuals with NCGS.

Hypothesis:

We hypothesize that expectation and/or actual intervention leads to symptom relief/impairment which affects mood (affective) changes in individuals with NCGS. More frequent and more severe symptoms will most likely lead to a more negative mood while fewer symptoms will lead to a more positive mood, measured by the PANAS.

3. STUDY DESIGN

The negative expectancy of consuming gluten on overall symptoms in individuals with NCGS will be investigated in a multicentre, randomized, double-blind, controlled intervention study. Participants will first be randomized into a group told that they will receive gluten-containing bread (E+) or gluten-free oat bread (E-). Subsequently, within each arm, participants will be randomized to gluten-containing oat bread (G+) or gluten-free oat bread (G-), which they will receive during the test day (see also Figure 2). An intervention of 1-day has been chosen as most symptoms develop within 6 hours in 72% of NCGS subjects (see also inclusion criteria) (14). In this respect, an 8 hours follow-up is sufficient to pick up changes in acute overall symptoms and to keep the study protocol feasible for participants. Additionally, the risk of a single consumption of gluten-containing bread for breakfast and lunch is negligible. Moreover, longer treatment periods would increase the burden for the participants and might lead to higher non-adherence rates. Nonetheless, a follow-up period of 2 days is included to monitor the effects of the 1-day bread intervention and the disappearance of the symptoms during these days.

[figure not shown]

Figure 2. Study design. (E- = Expectancy of getting gluten-free bread, E+ = Expectancy of getting gluten-containing bread, G+ = actual gluten-containing bread, G- = actual gluten-free bread).

Participant recruitment will start after the Medical Research Ethics Committee (METC) of Maastricht University Medical Center+ (MUMC+) has approved the study according to the revised version of the Guidelines of the Declaration of Helsinki (64th WMA General Assembly, Fortaleza, Brazil, October 2013). The study will be executed according to International Conference on Harmonisation (ICH) and Good Clinical Practice (GCP) guidelines.

Recruitment (and test days) will take place via MUMC+, Amsterdam University Medical Center (UMC) location VUmc and Wageningen University & Research (WUR). Participants will be recruited via the outpatient clinic (including the "stadspoli" or local GP practices) of the gastroenterology department and of the dietetics department of the participating study sites. Eligible individuals with NCGS will be given the patient information brochure by their treating physician or dietitian during their visit to the outpatient clinic. Furthermore, volunteers will be recruited by means of advertisements on the website of the "Prikkelbare Darmsyndroom Belangenvereniging", "Coeliakie vereniging", local and faculty newspapers, and social media, as well as by using posters in publicly accessible sites such as the hospital, university, health centres, pharmacies, gyms, bakeries and relevant shops (such as "the Bisschopsmolen" in Maastricht (http://www.bisschopsmolen.nl) and e.g. restaurants serving gluten-free meals), www.onderzoeksmachine.nl and the website ("see also document "E3 Advertentietekst NL64850.068.18 Versie2.0 02-10-2019").

Lists available in the participating centres, with potential eligible subjects (e.g. IBS, NCGS/NCWS and controls) who have previously indicated that they can be contacted about future studies, will also receive one single mailing containing the advertisement text with the study information. This mail will be sent by the local administrator of the database or local researcher of the participating centre. Potentially interested volunteers will contact the coordinating researcher by e-mail or telephone and will subsequently receive the written information brochure by e-mail or regular mail.

Furthermore, the recruitment website Proefpersonen.nl (https://www.proefpersonen.nl), which is facilitated by the company Link2Trials, will be used for recruiting and pre-screening eligible subjects. Volunteers enrolled in their database will be pre-screened by Link2Trials based on age. If they match these criteria, they will receive the advertisement text from Link2Trials. Furthermore, the advertisement text will be placed on their website, which is accessible to both volunteers already registered at Link2Trials and unregistered volunteers. Potentially interested volunteers will contact the coordinating researcher by e-mail or telephone, and will subsequently receive the written information brochure by e-mail or regular mail. Enrolment in the Link2Trials database is not necessary to obtain the researchers contact information, but is voluntary if subjects are interested in receiving information about other research.

In the participant information sheet (PIF), participants will be informed that they will be randomized to receive either the gluten-free or gluten-containing bread. On the test day, we will inform them that they will be allocated to one of the groups (to create expectancy), but they will not be informed that thereafter they will be randomized to receive gluten-free or gluten-containing bread as that would affect our primary outcome. The PIF, including the informed consent form is enclosed as separate document to the study protocol (see document "E1+E2_Proefpersoneninformatie_NL64850.068.18_Versie3.0_16-12-2020").

A time period of one week (minimum) is provided to decide whether the volunteer would like to participate. If the volunteer is interested and willing to participate, an informed consent form will be signed (co-signed by the investigator). After obtaining informed consent, a screening visit will be performed to assess the eligibility of the volunteer to participate in this study (based on the in- and exclusion criteria). However, when coeliac disease has not been excluded previously, a blood sample will be taken in an additional visit prior to the screening visit, but after signing informed consent. After inclusion, the total duration of the study will be 3 days. A total of 80 participants will complete the study.

The location of the test day will be planned together with the participants.

The study consists of (See Figure 3; Time line):

- 1. Screening visit (at MUMC+, Amsterdam UMC or WUR)
 - a. Coeliac disease test (at MUMC+, Amsterdam UMC or WUR)
- 2. Test day Day 1 (at MUMC+, Amsterdam UMC, WUR or otherwise (in consultation))
 - a. Randomization and treatment allocation
- 3. Follow-up questionnaires End of day 1, day 2 and 3
- 4. Debriefing (by mail), when all 80 participants have completed the study.

3.1 Screening visit

A screening visit will be performed to assess the eligibility of the volunteers to participate in this study. First, in- and exclusion criteria will be checked. Participants must have an overall symptom score for gastro-intestinal symptoms below or equal to 30mm in VAS-score over the last week (see "F1.1_Screeningsvragenlijst_WoWstudy_Versie1.1_04-04-2018") in order to participate in this study, after a gluten-free or gluten-restricted diet for at least one week. Thereafter, several baseline parameters will be assessed by means of questionnaires to obtain information about general health (e.g. personal history of medical and psychiatric illness (e.g. pregnancy), lifestyle, weight and height, adherence to gluten-free diet and general health (see paragraph 7.3)).

Furthermore, participants will be asked to give permission to contact their general practitioner (GP) for previous serologic examination(s) to exclude coeliac disease (e.g. anti-tTG IgA test or upper GI endoscopy). Serological tests (i.e. anti-tTG IgA) to rule out coeliac disease will be carried out during a visit prior to the screening visit, if tests to exclude coeliac disease have not been done before and if participants still consume traces or very low amount of gluten (as defined by the Biagi questionnaire) in their current diet. Volunteers will only be eligible when coeliac disease is sufficiently ruled out by means of serologic tests and if they meet the in/exclusion criteria. The blood sample (via venepuncture) for anti-tTG IgA will be taken prior to the screening visit and the results can take up to approximately 7 days. In the exceptional case of a positive test, the participant cannot participate in this study and their GP will be informed (see also IC form). To prevent us from collecting additional data from a non-eligible participant, it is preferred to have the test results available before the screening visit.

The screening visit will require approximately 60 minutes and will take place at the MUMC+, Amsterdam UMC or WUR, The Netherlands. The serological test visit requires an additional visit of 20 minutes.

3.2 Test day (Day 1)

On the test day, upon arrival in MUMC+, Amsterdam UMC or WUR, the participants will be informed by the researcher(s) that they have been allocated to a specific group (*i.e.* E+ or E-). They will then receive either gluten-containing (G+) or gluten-free (G-) oat bread. The participant and the investigator will both be blind to the actual study intervention the participant will receive, *i.e.* the gluten-containing (G+) or gluten-free bread (G-) within each of the expectancy groups (See Figure 2).

This randomization results in 4 groups:

Group 1: Participants with the expectation of receiving gluten-free bread but actually receiving gluten-containing bread during the test day (E-, G+).

Group 2: Participants with the expectation of receiving gluten-free bread and actually receiving gluten-free bread during the test day (E-, G-).

Group 3: Participants with the expectation of receiving gluten-containing bread and actually receiving gluten-containing bread during the test day (E+, G+).

Group 4: Participants with the expectation of receiving gluten-containing bread but actually receiving gluten-free bread during the test day (E+, G-).

During the test day, participants are asked to come to the MUMC+, Amsterdam UMC or WUR in a fasted state at 8.00AM. Before the participants are informed about which group they are assigned to, they will first have to fill in the symptom questionnaire and the positive and negative affective scale (PANAS) as baseline measurements. Then (± 8.15 AM) they will be informed that they have been allocated to the gluten-containing or gluten–free groups (i.e. creating expectancy, E- or E+) and at 8.30AM they have to consume 2 slices of study bread for breakfast and at 12.30PM a further 2 slices for lunch. All slices can be prepared with margarine plus cooked ham, or cheese, or marmalade (one standardised portion of one topping per slice, all gluten-free). Furthermore, they will be allowed to drink coffee, tea or water (ad libitum) during the test day. Other foods or drinks are not permitted during the test day until 4.30PM. During the test day, the participants are free to do what they want to (watching TV, reading, working, possibly take a walk), provided that they complete the questionnaires every hour.

Frozen packages of bread portions for the test day will be provided by European Bakery Innovation Centre, Papendrecht, The Netherlands, with a label that refers to the "expectancy" arm, but the actual treatment is blinded. Participants will be asked to report their GI symptoms, extra-intestinal symptoms, stool characteristics, and the PANAS in an electronic diary at baseline (at 8.00AM) and every hour till 4.30PM. After 4.30PM, participants will go home and will be allowed to eat freely as normal. During the study visits and telephonic contacts, the presence of serious adverse events will be checked. Participants will also be instructed to contact the researcher if their health status changes.

If participants are unable to stay at the MUMC+, Amsterdam UMC or WUR the entire day, they will receive the breakfast and the baseline questionnaire at the study location and can do the follow-up (*i.e.* completing the hourly questionnaire and consuming the study lunch) at home or at work, provided that all hourly questionnaires will be completed on the same tablet or notebook. If necessary, a study tablet will be provided for the test day. Subjects will receive a text message 5 minutes before each timepoint they have to fill in a questionnaire and will be informed that time of completion will be logged. Furthermore, participants have to adhere to the dietary restrictions. If possible, participants consume the study lunch in the presence of the researcher. Alternatively, participants are asked to provide pictures as proof of completely consuming the study lunch. The starting time of the test day can be flexible (before 9.00AM) and results in a shift of all time points, therefore it does not affect the structure of the test day. Any alterations in the test day (e.g. location of completing the hourly questionnaires) will be logged and taken into account during analyses.

3.3 Follow-up (end of day 1, day 2 and 3)

During the follow-up days participants will resume to their normal dietary habits, which is their usual gluten or wheat restricted/gluten-free diet, or the gluten-free/gluten-restricted diet they started at the beginning of the study. Furthermore, participants will be asked to complete the end of the day questionnaire (between 10.00-12.00PM), consisting of the daily symptom questionnaire, stool diary, and the PANAS.

3.4 Debriefing

On completion of the study, participants will be debriefed, but to avoid spread of information and bias in the data, the deception associated with the intervention and expectation as well as the aim of the study will only be disclosed after all participants (n=80) have completed the study. If there are any questions after the debriefing, participants can contact the research team at any time (contact details will be given via the debriefing mail). The debriefing information is available in document (see "E4 Debriefing NL64850.068.18 Versie1.2 12-03-2019").

[figure not shown]

Figure 3. Time line study

4. STUDY POPULATION

4.1 Population (base)

People in the general population with NCGS will be recruited to participate in this study.

4.2 Inclusion criteria

In order to be eligible to participate in this study, a subject must meet all of the following criteria:

- Develops self-reported GI symptoms within 8 hours after a single intake of glutencontaining products, without a diagnosis of an organic GI disease;
- Aged between 18-70 years;
- Following of willing to follow a gluten-free or gluten-restricting diet (based on a gluten-free dietary compliance questionnaire of Biagi et al. (only group 2, 3 and 4 will be eligible), see also "F1.2_Biagi vragenlijst naleving glutenvrij dieet_WoWstudy_Versie1.1_28-03-2018") for at least 1 week prior to study participation and willing to continue with this throughout the study;
- Asymptomatic or only mildly symptomatic (overall (GI) symptom score with VAS ≤ 30mm) while on the gluten-free diet;
- Willing to participate in a study in which they have to consume 4 slices of glutencontaining or gluten-free bread for breakfast and lunch during the test day;
- Willing and able to give written informed consent and to understand, participate and comply with the research project requirements.

4.3 Exclusion criteria

Participants who meet any of the following criteria will be excluded from participation in this study:

- Coeliac disease;
- Wheat allergy;
- Presence of an organic GI disease (such as inflammatory bowel disease) or other disease which may interfere with NCGS symptoms (upon judgment of the physicianclinical investigator ([name], Gastroenterologist MUMC+, and/or in consultation with clinicians/PI prof. [name] or prof. [name], when applicable));
- Previous major abdominal surgery or radiotherapy interfering with GI function:
 - Uncomplicated appendectomy, cholecystectomy and hysterectomy allowed unless within the past 6 months;

- Other surgery may be allowed based upon judgment of the physician-clinical investigator ([name], Gastroenterologist MUMC+), who will decide on inor exclusion based upon the surgery applied;
- Use of medication potentially influencing GI function and/or NCGS symptoms is allowed, provided that dosing has been stable for > 6 weeks before enrolment;
- Administration of antibiotics, probiotic or prebiotic supplements, investigational drugs or participation in any scientific intervention study, which may interfere with this study (to be decided by the principle investigator), in the 14 days prior to the study
- Excessive use of alcohol (>15 alcoholic units per week), or other drugs;
- Plan to lose weight or follow a specific diet within the study period;
- Any malignancy;
- Pregnancy or breastfeeding;
- Insufficient fluency of the Dutch language.

PM: Non-postmenopausal women will not be planned for the test day during menstrual bleeding.

4.4 Sample size calculation

Sample size calculation is based on our primary outcome measure, the overall symptom score, using a visual analogue scale (VAS). Since no data of overall symptom score based on expectancy in an NCGS population are available, we based our sample size calculations on a well-designed study most comparable to the present study by Biesiekierski et al. (2013) (17). In that study, the effects of gluten on GI symptoms in patients with NCGS after dietary reduction of fermentable, poorly absorbed, short chain carbohydrates (17) were examined. They reported an increase in mean overall symptom score after the ingestion of either 16g gluten/day (high-gluten arm) of 10.3mm in VAS-score with a standard deviation of 12.8mm (data obtained by requesting raw data from author (17)). In the study of Biesiekierski et al. (2013) a change of 20mm in VAS of overall symptom score was considered clinically relevant. Since our study has a different study design in which expectancy may play a major role and symptom scores may increase less, we deem an overall symptom difference in VAS-score of 15mm to be clinically relevant. Using a difference in overall mean symptoms of 15mm with a standard deviation of 12.8mm, power of 80% and two-sided alpha of 0.05, a sample size of 20 participants per group are required. So, a total sample size of 80 participants is required.

In addition, in order to account for potential drop outs due to drop-out after randomisation and during the test day for a reason other than intolerable symptoms, we ask permission to include max 5% (*i.e.* 4) extra participants, resulting in maximal 84 participants in total. Power analysis was conducted in the statistical power analysis program "G*power, version 3.1 for Macintosh" (19).

Version number: 3.0, date 16-12-2020

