9. STATISTICAL ANALYSIS

Statistical analyses will be carried out using IBM SPSS statistics 23.0 for Macintosh (Chicago IL, USA) and GraphPad Prism 6.0 for Macintosh (La Jolla, CA, USA). Baseline characteristics (including the outcomes of the questionnaires at baseline) will be analysed and summarized using descriptive statistics. Dichotomous variables will be presented as percentages and will be analysed using the Chi-square test. A Fisher exact test will be performed if necessary. Normality of continuous or ordinal variables will be evaluated by the Kolmogorov-Smirnov test and histograms for normality of the distribution. These variables will be analysed with the Wilcoxon signed-ranked test, when the distribution of the variables is non-parametric. If the variables are normally distributed a paired t-test will be performed. The independent variables will be analysed with the Mann-Whitney test if the distribution of the variables is nonparametric. If the variables are normally distributed an independent sample t-test will be done. Correlations will be assessed according to Spearman or Pearson and regression analyses will be done. An intention-to-treat analysis (ITT) will be conducted for all outcomes. All data will first be examined for accuracy of data-entry and missing values. A p-value < 0.05 is considered to be statistically significant. A similar study will be performed at the University of Leeds (United Kingdom), which will eventually provide us with the opportunity to compare the outcomes. Data will be analysed for each study site separately and also together using study site as a factor in the analysis.

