9.1 Primary and secondary study parameter(s)

The main research question will be analysed by means of repeated measures univariate analyses of variance (ANOVA) with Expectancy ("gluten-containing" vs. "gluten-free") and Gluten ("gluten-containing bread" vs. "gluten-free bread") as between-subjects factors and Time (baseline and after intervention) as repeated measure factors on the several dependent measures including changes in overall (GI) symptom score, gastro- and extraintestinal symptoms, positive and negative affective parameters, and well-being. Only significant main- or interaction effects revealed by these procedures will be further examined by post-hoc univariate tests, corrected for multiple comparisons.

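### Section 4.4: the stated inputs give 13 participants per group for the primary two-group comparison, not 20, so a stated figure is wrong or a test or adjustment goes unmentioned

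*Protocol*

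**What the plan says.** Section 4.4 gives the full set of inputs for a comparison of means. The effect and spread are given as: "Using a difference in overall mean symptoms of 15mm with a standard deviation of 12.8mm". The error rates and the result follow in the same sentence: "a standard deviation of 12.8mm, power of 80% and two-sided alpha of 0.05, a sample size of 20 participants per group are required". The result is 20 per group and 80 in total, calculated in G*Power 3.1. The statistical test is not named. Up to four further participants for drop-out are added after the 80, for a maximum of 84.

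Section 2 (caption of Figure 1) ties the primary objective to one pair of groups, E-G- and E+G-.

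On significance, section 9 says: "A p-value < 0.05 is considered to be statistically significant". Section 9.1 plans a repeated-measures ANOVA with Expectancy and Gluten as factors; only significant main or interaction effects "will be further examined by post-hoc univariate tests, corrected for multiple comparisons". Neither section refers back to the sample size.

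**The concern.** An effect of 15 mm against an SD of 12.8 mm is more than one standard deviation. At 80% power and two-sided alpha 0.05, a difference that large normally needs well under 20 per group. So the four inputs and the result do not appear to belong to the same calculation.

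What is at stake is the stated justification. The ethics committee and later readers are told that 80 participants are required at 80% power. If the inputs are right, the power statement is wrong by about 15 percentage points. If the power is right, one of the other inputs, or the test behind the number, is not the one reported. Either way, the calculation cannot be reproduced from the text.

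**Working it through.** **Inputs, all from section 4.4:** difference 15 mm; SD 12.8 mm; power 80%; two-sided alpha 0.05; equal groups. The comparison of two groups comes from section 2.

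**Standardised effect:** d = 15 / 12.8 = 1.172.

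**Attempt to reproduce 20, normal approximation:** n = 2(1.960 + 0.842)² / d² = 2 × 7.85 / 1.373 = 11.4, so 12 per group.

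**Two-sample t-test, exact:** power is the probability that a noncentral t with 2(n - 1) degrees of freedom and noncentrality d√(n/2) exceeds the critical value in absolute size.

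| n per group | noncentrality | critical t | power |
|---|---|---|---|
| 12 | 2.870 | 2.074 | 78.3% |
| 13 | 2.988 | 2.064 | 81.8% |
| 20 | 3.706 | 2.024 | 95.1% |

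The solution for 80% is n = 12.47, so 13 per group and 4 × 13 = 52 in total. The stated 20 is not reproduced. The gap is 7 per group, or 28 of 80, which is too large for rounding.

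**Does another standard choice at alpha 0.05 and 80% power give 20?**

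| Choice | n per group |
|---|---|
| One-sided t-test | 10 |
| Mann-Whitney, efficiency 3/π (12.47 / 0.955 = 13.06) | 14 |
| Mann-Whitney, minimum efficiency (12.47 / 0.864 = 14.43) | 15 |
| Paired t-test | 8 |
| SD multiplied by √2 | 24 |
| Pairwise contrast, error pooled over four groups | 12 |
| 2×2 main effect | 7 |
| 2×2 interaction of 15 mm | 24 |
| Four-group omnibus ANOVA, means 0, 0, 15, 15 | 9 |
| Four-group omnibus ANOVA, means 0, 0, 0, 15 | 12 |
| Four-group omnibus ANOVA, means 0, 7.5, 7.5, 15 | 17 |

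None of these gives 20. Drop-out does not explain it either: it is added after the 80, and inflating 13 by 5% gives only 14. The other two differences mentioned in section 4.4 do not give 20 with the same SD: 10.3 mm needs 25.2, so 26, and 20 mm needs 7.5, so 8.

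**What would give 20?** Changing one or two inputs, with the t-test:

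| Change | n per group |
|---|---|
| Power 95%, alpha 0.05 | 19.94, so 20 |
| Power 90%, alpha 0.025 | 19.39, so 20 |
| Power 80%, alpha 0.05/6 = 0.0083 | 19.44, so 20 (81.5% power) |
| Difference about 11.6 mm (0.909 × 12.8), power 80%, alpha 0.05 | about 20 |
| SD about 16.5 mm (15 / 0.909), power 80%, alpha 0.05 | about 20 |

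Here 0.909 is the standardised effect that 20 per group detects with 80% power at alpha 0.05.

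One route keeps all four stated inputs. A four-group omnibus ANOVA with means 0, 7.5, 7.5, 15 has f = 5.30 / 12.8 = 0.414 and needs 16.9 per group; dividing by 0.864 for a rank test gives 19.5, so 20.

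**The case against.** The best defence is that section 4.4 names no test, so a t-test is the reviewer's choice. The last route above reaches 20 without touching any stated input, section 9 allows non-parametric tests, and section 9.1 plans a four-cell ANOVA. This stands as far as it goes: the number may come from a legitimate calculation. But that calculation needs a particular pattern of four means and an efficiency factor, neither of which is in the protocol, and it does not address the two-group comparison named as primary. It moves the fault from a wrong figure to an unstated method; the text still does not support the number.

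The second defence is that the error runs in the safe direction. That is correct, and it limits the weight of the point.

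Two stronger readings are tempting, and neither is supported.

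- A reader might infer that the size was really built on a Bonferroni alpha of 0.0083 over the six pairwise comparisons of four groups, and that a p-value between 0.0083 and 0.05 would then be positive by one rule and negative by another. No section mentions six comparisons or 0.0083, and several other input sets also give 20. Section 9.1 attaches its correction to post-hoc tests and does not link it to the sample size. Significance is decided by the rules in sections 9 and 9.1, not by an alpha used for sizing. How the correction applies to E+G- vs E-G- is a separate question that would remain at any sample size.
- A reader might infer that 28 participants too many are being recruited. The documents do not show that the inputs, rather than the 20, are right. The secondary objectives also use all four groups, and a 2×2 interaction of 15 mm would need 24 per group on the same inputs.

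**Conclusion.** The point holds in a limited form. For the primary two-group comparison, the stated 15 mm, SD 12.8 mm, 80% power and two-sided alpha 0.05 give 13 per group, not 20. With 20 per group the power for 15 mm is 95.1%, or 80% for 11.6 mm. So at least one of the power, alpha, SD and difference is misreported, or a test or adjustment was used and not stated. The protocol does not allow the reader to tell which.

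This rests on a two-sample t-test with equal groups and a common SD. A rank test moves the requirement only to 14 or 15. On the protocol's own assumptions the trial is not underpowered. The point calls for a reporting correction and does not put the design or the primary conclusion in doubt.

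**What to change.** Keep 80 participants. Retrieve the original G*Power run and correct section 4.4 to state the test, difference, SD, alpha, power and any adjustment actually entered.

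- If the stated alpha, SD and difference stand, give the power at 20 per group as about 95% for 15 mm, and add that this size has 80% power for 11.6 mm.
- If the run used a different SD or difference, report that value and its source.
- If it used a multiplicity-corrected alpha, state it in section 4.4 and make sections 9 and 9.1 consistent with it.
- If it used a four-group or non-parametric calculation, name it and give the assumed means and inflation factor.

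Section 4.4 should not be used to introduce a new testing rule for E+G- vs E-G-; any such rule belongs in section 9.1. The cost is a sentence or two in section 4.4, with a matching edit to sections 9 and 9.1 only in the multiplicity case, and no extra participants.
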